5.2 SERIOUS ADVERSE EVENTS

The term “Serious Adverse Event” (SAE) is defined in 21 CFR 312.32 as follows: “An adverse event or suspected adverse reaction is considered serious if, in the view of either the investigator or the sponsor, it results in any of the following outcomes: Death, a life-threatening adverse event, inpatient hospitalization or prolongation of existing hospitalization, a persistent or significant incapacity or substantial disruption of the ability to conduct normal life functions, or a congenital anomaly/birth defect. Important medical events that may not result in death, be life-threatening, or require hospitalization may be considered serious when, based upon appropriate medical judgment, they may jeopardize the patient or subject and may require medical or surgical intervention to prevent one of the outcomes listed in this definition. Examples of such medical events include allergic bronchospasm requiring intensive treatment in an emergency room or at home, blood dyscrasias or convulsions that do not result in inpatient hospitalization, or the development of drug dependency or drug abuse.”

“Life-threatening” refers to an AE that at occurrence represents an immediate risk of death to the subject. An event that may cause death if it occurs in a more severe form is not considered life-threatening. Similarly, a hospital admission for an elective procedure is not considered a SAE.

5.3 ADVERSE EVENT REPORTING TO THE IND SPONSOR

AEs that meet SAE Reporting Requirements must be reported and submitted by the clinical site on an expedited basis to the IND Sponsor, VRC/NIAID/NIH, according to sponsor guidelines as follows:

- results in death
- is life threatening

- results in persistent or significant disability/incapacity
- requires unplanned inpatient hospitalization or prolongation of existing hospitalization
- is a congenital anomaly/birth defect in the offspring of a study subject
- is an important medical event that may jeopardize the subject or may require intervention to prevent one of the other outcomes listed above.

In addition, any event, regardless of severity, which in the judgment of the PI represents a SAE, may be reported on an expedited basis.

An investigator will communicate an initial SAE report within 24 hours of site awareness of occurrence to the IND Sponsor by email to the VRC Protocol Operations Office (Appendix I).

A written report by PI should be submitted to the IND Sponsor within 3 working days. In order for the IND Sponsor to comply with regulations mandating sponsor notification of specified SAEs to the FDA within 7 or 15 calendar days, the investigator must submit additional information as soon as it is available.

5.3.1 IND Sponsor Reporting to the FDA

It is the responsibility of the IND Sponsor to make the determination of which SAEs are “serious and unexpected suspected adverse reactions” (SUSARs) as defined in 21 CFR 312.32.

- *Suspected adverse reaction* means any AE for which there is a reasonable possibility that the drug caused the AE.
- *Unexpected Adverse Event* means an AE that is not listed in the Investigator’s Brochure or is not listed at the specificity or severity that has been observed.

All SUSARs, as determined by the IND Sponsor, will be reported to the FDA as IND Safety Reports and IND Safety Reports will be provided to the IRB.

The IND Sponsor will also submit an IND Annual Report of the progress of the investigation to the FDA as defined in 21 CFR 312.33.

5.4 REPORTING TO THE INSTITUTIONAL REVIEW BOARD

5.4.1 Unanticipated Problem Definition

An unanticipated problem (UP) is defined as any incident, experience, or outcome that meets all three of the following criteria:

- unexpected in nature, severity, or frequency in relation to the research risks that are described in the protocol, informed consent, Investigator’s Brochure, other study documents or in consideration of the characteristics of the subject population being studied; **and**
- related to participation in the research; **and**
- suggests that the research places subjects or others at a greater risk of harm (including physical, psychological, economic, or social harm) than was previously known or recognized.

Serious UP: An UP that meets the definition of a SAE or compromises the safety, welfare or rights of subjects or others.

An UP that is not an Adverse Event (UPnonAE) is an unanticipated problem that does not fit the definition of an AE, but which may, in the opinion of the investigator, involve risk to the subject, affect others in the research study, or significantly impact the integrity of research data. Such events would be considered a non-serious UP. For example, we will report occurrences of breaches of confidentiality, accidental destruction of study records or samples, or unaccounted-for study drug.

5.4.2 Protocol Deviation Definition

A protocol deviation is defined as any change, divergence, or departure from the IRB-approved study procedures in a research protocol. Protocol deviations are designated as serious or non-serious and further characterized as follows:

- Those that occur because a member of the research team deviates from the protocol.
- Those that are identified before they occur, but cannot be prevented.
- Those that are discovered after they occur.

Serious Protocol Deviation: A deviation that meets the definition of a SAE or compromises the safety, integrity of the data, welfare or rights of subjects or others.

5.4.3 Non-Compliance Definition

Non-compliance is the failure to comply with applicable NIH Human Research Protections Program (HRPP) policies, IRB requirements, or regulatory requirements for the protection of human subjects. Non-compliance is further characterized as serious, continuing or minor.

“Serious non-compliance” is defined as non-compliance that:

- Increases risks, or causes harm, to participants
- Decreases potential benefits to participants
- Compromises the integrity of the NIH-HRPP
- Invalidates the study data

“Continuing non-compliance” is non-compliance that is recurring.

“Minor non-compliance” is non-compliance that is neither serious nor continuing.

5.4.4 Expedited Reporting to the NIAID IRB

The following will be reported within 7 calendar days of investigator awareness:

- Serious and non-serious UP
- Deaths
- Serious protocol deviations
- Serious or continuing non-compliance
- SAEs that are possibly, probably, or definitely related to the research regardless of expectedness

The following waiver applies to reporting anticipated protocol deviations and expected UPnonAEs: Anticipated deviations in the conduct of the protocol will not be reported to the IRB unless they occur at a rate greater than anticipated by the study team. Expected AEs will not be

reported to the IRB unless they occur at a rate greater than that known to occur in healthy adults. If the rate of these events exceeds the rate expected by the study team, the events will be classified and reported as though they are unanticipated problems.

5.4.5 Annual Reporting to the NIAID IRB

The following will be reported to the NIAID IRB in summary at the time of Continuing Review:

- Serious and non-serious UPs
- Expected SAEs that are possibly, probably, or definitely related to the research
- SAEs that are not related to the research
- All AEs, except expected AEs granted a waiver of reporting
- Serious and non-serious Protocol Deviations
- Serious, continuing, and minor non-compliance
- Any trends or events which in the opinion of the investigator should be reported

5.5 SERIOUS ADVERSE EVENT REPORTING TO THE INSTITUTIONAL BIOSAFETY COMMITTEE (IBC)

The NIH Institutional Biosafety Committee (IBC) (Bethesda, MD) has the responsibility to review research using recombinant DNA for compliance with NIH Guidelines. In keeping with IBC requirements, any SAE reports sent to the IRB will be subsequently provided to the IBC by the investigators.

6. STATISTICAL CONSIDERATIONS

6.1 OVERVIEW

This is a Phase I, open-label, dose escalation study to evaluate the dose, safety, tolerability, and immunogenicity of VRC-FLUNPF081-00-VP vaccine alone or in prime-boost regimens with VRC-FLUDNA082-00-VP vaccine.

6.2 OBJECTIVES

The primary objectives are to evaluate the safety and tolerability of VRC-FLUNPF081-00-VP vaccine when administered as a single dose at 20 mcg, and to evaluate the safety and tolerability of two prime-boost vaccine regimens:

- VRC-FLUNPF081-00-VP administered at 60 mcg by repeat dosing at Day 0 and Week 16.
- VRC-FLUDNA082-00-VP vaccine administered at 4 mg at Day 0 and VRC-FLUNPF081-00-VP administered at 60 mcg at Week 16.

Secondary objectives include the evaluation of antibody responses to two prime-boost vaccine regimens in healthy adults at two weeks after the boost vaccine for each treatment and age group.

Exploratory objectives include the evaluation of the magnitude, the specificity, and the frequency of H2-specific T-cell, B-cell responses and antibody responses at indicated time points throughout the 40 weeks of the study.

6.3 ENDPOINTS

6.3.1 Primary Endpoints: Safety

Assessment of product safety will include clinical observation and monitoring of hematological and chemical parameters. Reactogenicity will be closely monitored for 7 days after each injection and safety evaluated by clinical visits throughout 40 weeks. See Section 4.2 and Appendix II for details and specified time points.

The following parameters will be assessed for all study groups:

- Occurrence of solicited local reactogenicity symptoms for 7 days following each injection
- Occurrence of solicited systemic reactogenicity symptoms for 7 days following each injection
- Change from baseline in safety laboratory measures
- Occurrence of AEs of all severities through the “Week 4” visit after each injection
- Occurrence at any time throughout the study of SAEs or new chronic medical conditions that require ongoing medical management.

6.3.2 Secondary Endpoints: Immunogenicity

The principal immunogenicity endpoints are magnitude and frequency of antibody responses measured by neutralization assay and/or HAI assay at Week 0, at 4 weeks (W4) after the prime vaccination, and at 2 weeks (W18) after the boost vaccination.

6.3.3 Exploratory Endpoints: Immunogenicity

The magnitude, the specificity, and the frequency of H2-specific neutralizing antibodies that are four-fold greater than baseline at 2 weeks after the boost for each group will be evaluated.

Evaluation of antibody and T cell responses at time points throughout the study will be completed as an exploratory evaluation.

For the H2 neutralization assay, a positive response for a subject is defined as the subject achieving a four-fold rise in the H2-specific neutralization antibody titer from baseline.

6.4 SAMPLE SIZE AND ACCRUAL

Recruitment will target 50 healthy adult participants 18 to 70 years of age. Adults born between 1966 and 1969 will be excluded from the trial.

6.4.1 Power Calculations for Safety

The goal of the safety evaluation for this study is to identify safety concerns associated with injections of the investigational vaccines. Primary sample size calculations for safety are expressed in terms of the ability to detect serious adverse experiences. Other sample size calculations for comparing the two vaccination groups on adverse experiences are similar to the calculations for immunogenicity (Section 6.4.3).

The ability of the study to identify SAEs will be expressed in terms of the probability of observing a certain number of SAEs. Useful values are the minimum true rate such that the probability of observing at least one event is at least 90%, and the maximum true rate such that the probability of not observing any event is at least 90%.

For Part I (*dose-escalation*) within each group (n=5), there is a 90% chance to observe at least 1 SAE if the true rate is at least 0.369 and over 90% chance to observe no SAE if the true rate is less than 0.021.

For Part II (*prime-boost*) within each group (n=10), there is over a 90% chance to observe at least 1 SAE if the true rate is at least 0.206 and over a 90% chance to observe no SAE if the true rate is no more than 0.010.

Probabilities of observing 0 or more than 1 SAE within each group are presented in **Table 6-1** for a range of possible true event rates. These calculations provide a complete picture of the sensitivity of this study design to identify potential safety problems with the vaccine.

Table 6-2 gives the upper and lower bounds for 95% exact binomial confidence intervals of the true SAE rate at all possible numbers of events within each group (n=5 and n=10).

For Part I (n=5): If none of the 5 participants receiving the vaccines experience SAEs, the 95% exact 2-sided upper confidence bound for the SAE would range from 0 to 0.52.

For Part II (n=10): If none of the 10 participants receiving the vaccines experience SAEs, the 95% exact 2-sided upper confidence bound for the SAE rate is 0.308.

Table 6-1: Probability of Events for Different Safety and Immunogenicity Scenarios

True Event Rate	Part I (dose-escalation): N=5		Part II (prime-boost): N=10	
	Pr (observing 0 event)	Pr (observing more than 1 event)	Pr (observing 0 event)	Pr (observing more than 1 event)
0.01	0.951	0.001	0.904	0.004
0.02	0.904	0.004	0.817	0.016
0.05	0.774	0.023	0.599	0.086
0.1	0.590	0.081	0.349	0.264
0.15	0.444	0.165	0.197	0.456
0.2	0.328	0.263	0.107	0.624
0.3	0.168	0.472	0.028	0.851
0.4	0.078	0.663	0.006	0.954
0.5	0.031	0.813	0.001	0.989

Table 6-2: 95% Confidence Intervals for the True Rate at All Possible Observed Rates within a Group (n=5 and n=10)

	Part I: N=5 95% Confidence Interval			Part II: N=10 95% Confidence Interval	
Observed Rate	Lower Bound	Upper Bound	Observed Rate	Lower Bound	Upper Bound
0/5	0	0.522	0/10	0	0.308
1/5	0.005	0.716	1/10	0.003	0.445
2/5	0.053	0.853	2/10	0.025	0.556
3/5	0.147	0.947	3/10	0.067	0.652
4/5	0.284	0.995	4/10	0.122	0.738
5/5	0.478	1	5/10	0.187	0.813
			6/10	0.262	0.878
			7/10	0.348	0.933
			8/10	0.444	0.975
			9/10	0.555	0.997
			10/10	0.692	1

6.4.2 Power Calculations for Immunogenicity

Table 6-2 is applicable to the immunogenic response rates, and gives the exact 95% confidence interval of the true response rate over possible number of responses out of the 5 and 10 subjects.

Table 6-1 gives the probabilities of observing 0 or more than 1 response over a range of underlying response rates.

6.4.3 Power for Comparison

As exploratory analyses, we will compare the four groups in Part II of the study for possible differences in immunogenicity; a simple comparison on the positive response rate will be used. **Table 6-3** gives the power of Fisher's exact test to compare any two schedules over a range of possible response rates. It indicates that a comparison between two groups is not powered by the study design with 10 samples per group. **Table 6-3** also gives the power of Fisher's exact test when the age cohorts within each group are combined, resulting in a comparison between two groups with 20 samples per group. It indicates that with age cohorts combined, the comparison would be powered for larger differences between groups.

Table 6-3: Power to Detect Difference in Response Rates between the groups in Part II by Fisher's Exact Test, Where Both Groups are of Size n=10 or n=20

	Group 4A (N=10)						
Group 3A (N=10)		0.1	0.2	0.3	0.4	0.5	0.6
	0.1		1	6	15	30	47
	0.2	1		2	6	13	25
	0.3	6	2		2	5	12
	0.4	15	6	2		2	5
	0.5	30	13	5	2		2
	0.6	47	25	12	5	2	
	Group 4B (N=20)						
Group 3B (N=20)		0.1	0.2	0.3	0.4	0.5	0.6
	0.1		7	24	49	74	91
	0.2	7		6	19	41	65
	0.3	24	6		6	16	35
	0.4	49	19	6		5	14
	0.5	74	41	16	5		5
	0.6	91	65	35	14	5	

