3.2 SECONDARY OBJECTIVES

- To evaluate the antibody response to two prime-boost vaccine regimens in healthy adults:
 - 1) DNA A/Sing vaccine administered at 4 mg IM via needle-free injection device at Day 0 followed by HA-F A/Sing vaccine administered at 60 mcg IM via needle and syringe at Week 16.
 - 2) HA-F A/Sing vaccine administered at 60 mcg IM via needle and syringe by repeat dosing at Day 0 and Week 16.
- To compare the magnitude and the frequency of H2-specific antibody response as measured by HAI at four weeks after the prime vaccine and two weeks after the boost vaccine for each treatment and age group.

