4.2.3 Enrollment and Randomization

Day 0 is defined as the day of protocol enrollment and first injection for all groups. Protocol-specific eligibility is reviewed on Day 0 as part of the enrollment process, but eligibility evaluations conducted during a screening visit are routinely used for eligibility if evaluations are within the specified window prior to Day 0. However, if clinical assessment on Day 0 suggests significant changes may have occurred since the screening visit, then evaluations done on Day 0 are used for eligibility. Day 0 evaluations and medical history prior to the first injection are the baseline for subsequent safety assessments.

Part I includes staged enrollment with required interim safety reviews before proceeding with the next dose group. In Group 1, five subjects will be enrolled with no more than one subject per day. Following dose escalation review, five subjects will be enrolled in Group 2 with no more than one subject per day. An internal safety review will determine whether enrollment can begin in Part II.

In Part II subjects will be stratified by age and randomized equally into Group 3 and Group 4. Neither the clinic staff nor the subjects will know in advance which group will be assigned to the enrollees in the study. The Protocol Statistician will prepare the randomization plan in advance and provide it to the site Pharmacy and Data Management Center.

The pharmacy database and study randomization will be set up prior to opening the study to accrual. The group assignment will become known to the staff and subject immediately after completing the electronic enrollment into the study on Day 0. The visit schedule is based on intervals of time after each study injection (Appendix II).

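### Section 3.2 promises a comparison of antibody magnitude, but the only between-group method planned compares responder rates and, when age cohorts are pooled, ignores the randomisation stratum

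*Combined protocol and SAP*

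**What the plan says.** - **Objective.** Section 3.2 includes "To compare the magnitude and the frequency of H2-specific antibody response as measured by HAI", four weeks after the prime and two weeks after the boost. Section 6.3.2 makes magnitude and frequency the principal immunogenicity endpoints. Section 1.3 says the DNA-prime regimen will be compared with the HA-F-prime regimen.
- **Randomisation.** Section 4.2.3: "In Part II subjects will be stratified by age and randomized equally into Group 3 and Group 4". Section 1.5 explains that the age cohorts (18–47 and 52–70) were chosen for their likely difference in prior H2 exposure.
- **Between-group method.** Section 6.4.3 announces an exploratory immunogenicity comparison among the four Part II subgroups, for which "a simple comparison on the positive response rate will be used". Power is tabulated in Table 6-3 for pairs of assumed rates, with Fisher's exact test as the method. The section concludes that "a comparison between two groups is not powered by the study design with 10 samples per group", but that with age cohorts combined (20 per group) the power suffices for larger differences.
- **Titres.** For continuous readouts, Section 6.5.4 plans graphs and tables, possibly on a log scale. It gives no test, model or interval for a difference between groups. Subjects with a positive antibody response at baseline are left out of the final immunogenicity analysis.

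**The concern.** Part II contains the trial's one randomised contrast: DNA prime versus HA-F prime, each followed by an HA-F boost. The objective asks whether the regimens differ in the size of the response as well as in the share of responders. The stated method addresses only the second question. Cutting titres into responder and non-responder costs a lot of information at 10 or 20 subjects per group. Pooling the two age cohorts without stratifying can cost more if they respond differently.

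Two things are at stake. Part of a stated secondary objective has no planned inference, and any titre comparison would have to be chosen after the data are seen. The planned comparison is also less sensitive than the samples allow.

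**Working it through.** **1. Reproduce Table 6-3.** Inputs from Section 6.4.3: 10 or 20 per group, true rates 0.1 to 0.6, Fisher's exact test. The plan states neither alpha nor sidedness; I assume two-sided 0.05. Power is the sum of Bin(a; n, p1) × Bin(b; n, p2) over all outcome pairs (a, b) with Fisher p ≤ 0.05. All 60 off-diagonal cells agree within 0.5 percentage points. Examples:

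- n=10, 0.1 vs 0.6: 47.4% (table 47).
- n=20, 0.1 vs 0.5: 74.2% (74).
- n=20, 0.1 vs 0.6: 90.8% (91).
- n=20, 0.2 vs 0.6: 65.0% (65).

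One-sided 0.025 gives nearly the same table; one-sided 0.05 is off by up to 19 points. The arithmetic of Table 6-3 is right.

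**2. Same scenarios on the log-titre scale.** Assume log2 response is normal with a common SD in both groups, shifted so that the same cut-off yields the tabulated responder rates. The standardised shift is d = z(p2) − z(p1), with z the normal quantile. Two-sample t-test power uses the noncentral t with 2n − 2 degrees of freedom and noncentrality d√(n/2).

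- 0.2 vs 0.6: d = 0.253 + 0.842 = 1.095. At n=20 the noncentrality is 1.095 × √10 = 3.46 and power is 92%.
- 0.3 vs 0.6: d = 0.253 + 0.524 = 0.778 (unrounded quantiles). At n=20 the noncentrality is 2.46 and power is 67%.

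**3. Stress the normal assumption.** I also use simulated results with two-fold dilution steps, a detection floor, SD 1 to 2 log2 units, and either a Wilcoxon or a t-test.

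| Rates | n | Fisher | t-test, normal shift | With steps and floor |
|---|---|---|---|---|
| 0.1 vs 0.5 | 10 | 30% | 77% | 63–73% |
| 0.1 vs 0.6 | 10 | 47% | 90% | 81–86% |
| 0.2 vs 0.5 | 10 | 13% | 43% | 34–40% |
| 0.3 vs 0.6 | 10 | 12% | 38% | 32–35% |
| 0.1 vs 0.5 | 20 | 74% | 98% | 92–95% |
| 0.2 vs 0.5 | 20 | 41% | 74% | 65–67% |
| 0.2 vs 0.6 | 20 | 65% | 92% | 86–89% |
| 0.3 vs 0.6 | 20 | 35% | 67% | 60–62% |

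Table 6-3 has 15 distinct pairs of unequal rates. At n=10, 80% power is reached in 0 of 15 with Fisher and 1 of 15 with the idealised t-test. At n=20 it is reached in 1 of 15 and 4 of 15.

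**4. Age stratum.** With 10 per cell and the binary endpoint, I compare the pooled Fisher test with an exact test stratified by age. Rates are written younger/older.

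| Rates, one group vs the other | Pooled | Stratified |
|---|---|---|
| 0.5/0.5 vs 0.1/0.1 | 74.2% | 73.6% |
| 0.5/0.9 vs 0.1/0.5 | 59.9% | 73.6% |
| 0.3/0.9 vs 0.1/0.5 | 31.1% | 49.1% |

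On log titre with a true effect of 0.9 SD and 20 per group, adjusting for cohort changes power as follows: 80% to 80% with no age gap, 77% to 79% with a 0.5 SD gap, about 70–72% to 79% with 1 SD, and about 49–50% to 79% with 2 SD. The documents give no figure for the gap.

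**5. Baseline covariate.** Adjustment raises d to d/√(1 − r²), where r is the correlation of baseline with post-boost log titre. For 0.2 vs 0.5 at n=20, r from 0.3 to 0.7 gives 77% to 95%, against 74% unadjusted. The documents do not give r, and it may be low once baseline-positive subjects are removed.

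No dropout or exclusion is applied in any of these figures. Removing baseline-positive subjects would lower all of them, probably most in the 52–70 cohort.

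**The case against.** The strongest reply is that this is a Phase I trial with safety as its primary aim, and Section 6.4.3 calls the comparison exploratory. Section 6.2 words the secondary objective as evaluating the responses, without a comparison. Section 6.5.4 already provides exact confidence intervals for response rates and summaries of titres. This limits the weight of the point. It does not remove it, because Section 3.2 does promise a comparison of magnitude and nothing in the plan delivers one.

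A reader might also infer more than the documents support:

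- *That the lack of power at 10 per group is an artefact of Fisher's test.* It is not. Even the idealised t-test reaches 80% in only 1 of 15 scenarios, so the number of subjects is the main limit.
- *That the plan presents the whole design as unpowered.* It does not. Section 6.4.3 says the pooled comparison has power for larger differences, and Table 6-3 shows 91% at 0.1 versus 0.6.
- *That baseline titre is thrown away.* It enters through the four-fold-rise definition in Section 6.3.3 and the baseline-positive exclusion in Section 6.5.4. It is only not a covariate.
- *That the age stratum is always ignored.* Group 3A versus 4A and 3B versus 4B are within-stratum comparisons. Only the pooled one ignores it.
- *That Fisher's test is an error.* It is conservative here, with a maximum true size of 1.3% at n=10 and 2.5% at n=20 against the assumed 5%, but it is valid. Preferring a less conservative exact test is a matter of choice. Section 6.4.3 names Fisher's test for power; the analysis itself is described more loosely.

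**Conclusion.** The point holds as a mismatch between objective and method. Comparing magnitude is a stated secondary objective with no planned between-group analysis, and the pooled comparison omits the stratum used to randomise. An age-adjusted log-titre analysis would answer the objective with samples already scheduled.

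The gain matters mainly at 20 per group: about 27 points for 0.2 versus 0.6 (65% to 92%) and 32 points for 0.3 versus 0.6 (35% to 67%), or 21–24 and 25–27 points with dilution steps and a floor. These sizes rest on a two-sided 5% level, a normal shift matched to the responder rates, and no loss of subjects. At 10 per group most scenarios stay below 80% (43% at 0.2 versus 0.5), so the plan's statement there largely stands. Age adjustment gains nothing if the cohorts respond alike, and baseline adjustment may gain little after the exclusion.

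Separately, the lower block of Table 6-3 is labelled Groups 3B and 4B with N=20, although each has 10 subjects. The text of Section 6.4.3 shows that it describes the combined cohorts. This is clerical and changes no number.

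**What to change.** In Sections 6.4.3 and 6.5.4:

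1. Prespecify the comparison of log2 titre, Group 4 versus Group 3, at two weeks after the boost and at four weeks after the prime. Use a linear model with age cohort and log2 baseline titre as covariates, and report the geometric mean ratio with its 95% CI.
2. Add an age-stratified Wilcoxon (van Elteren) test as a check where titres fall below detection.
3. Keep the responder-rate comparison as supportive, and stratify it by age whenever the cohorts are pooled.
4. State alpha and sidedness.
5. Relabel the lower block of Table 6-3 as Groups 3 and 4 with age cohorts combined.

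The comparison can remain exploratory in status. The cost is wording and a little programming, with no added subjects, visits or samples. The downside is reliance on a log-normal working model, which the rank-based check covers.

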6.6 INTERVENTION ASSIGNMENTS

For Part I (*dose-escalation*): Subjects between 18-47 years will be assigned to the dose group that is open to accrual at the time of enrollment. When a subject is enrolled into a group but does not begin study injections or if a subject withdraws, a new eligible subject may be enrolled into the same group in order to complete the safety data set as planned.

For Part II (*prime-boost*): Subjects will be stratified by age and randomized equally into Group 3 or Group 4.

The subject and the study clinicians will be informed on the subject's randomization assignment upon completing of enrollment in Advantage Electronic Data Collection (AdEDC) system.

To decrease the potential for participant dropouts during the period between randomization and initial vaccination, randomization will occur on Day 0 after the study consent is signed and eligibility is confirmed. If subjects accrued to a study group do not complete the number of vaccinations and follow-up duration specified, then additional subjects may be accrued in that group.

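### For the Part II responder-rate comparison, Boschloo's exact test would give more power than Fisher's within the same 5% error limit, and the conclusion drawn from Table 6-3 for 10 per group should be limited to the differences it covers

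*Combined protocol and SAP*

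**What the plan says.** Section 6.4.3 introduces the comparison as exploratory: "As exploratory analyses, we will compare the four groups in Part II of the study for possible differences in immunogenicity". It uses the positive response rate, and Table 6-3 "gives the power of Fisher's exact test to compare any two schedules over a range of possible response rates". The grid runs from 0.1 to 0.6 in steps of 0.1, for 10 per group (one age cohort) and 20 per group (age cohorts combined). For 10 per group the text concludes: "It indicates that a comparison between two groups is not powered by the study design with 10 samples per group". For 20 per group it adds that larger differences would be powered. No significance level, sidedness, target power or expected response rate is given.

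Allocation is 1:1 (section 6.6: "Subjects will be stratified by age and randomized equally into Group 3 or Group 4"). Section 6.4.1 says that sample size calculations for "comparing the two vaccination groups on adverse experiences are similar to the calculations for immunogenicity". Section 6.5.4 takes subjects with a positive baseline antibody response out of the final immunogenicity analysis.

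**The concern.** Fisher's exact test conditions on the total number of responders. With 10 or 20 per group few outcomes are possible for each total, so the test cannot come near its nominal 5% and gives up power. In a design this small that loss is material, and an exact test that avoids it exists.

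The conclusion for 10 per group also reaches further than its table. No difference above 0.5 is tabulated, yet the sentence sets no limit on the size of the difference, whereas the statement for 20 per group is tied to larger differences. A reader would take it that no contrast within an age cohort can be detected reliably. The comparison is of some interest: section 3.2 lists comparing the frequency of HAI response by treatment and age group, four weeks after the prime and two weeks after the boost, as a secondary objective.

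**Working it through.** **Inputs.** The test, the group sizes (10 and 20) and the rates come from section 6.4.3, and 1:1 allocation from section 6.6. Two assumptions are needed: a two-sided 5% level, and 80% as the meaning of powered.

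**Method.** Let X ~ Bin(n, p1) and Y ~ Bin(n, p2) be independent. Power = Σ Pr(X=x)·Pr(Y=y) over all outcomes that the test rejects. True size = the maximum of the same sum over a common rate p1 = p2 = p.

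**Rejection regions at n=10** (plus mirror images):
- Fisher (two-sided p ≤ 0.05): 0 vs ≥5, 1 vs ≥7, 2 vs ≥8, 3 vs ≥9, 4 vs 10, 5 vs 10.
- Boschloo: order the outcomes by Fisher's p-value and use the largest cut-off that keeps the maximum size at or below 5%. The cut-off is 0.087; the next possible one, 0.141, would give 6.2%. The region is 0 vs ≥4, 1 vs ≥6, 2 vs ≥7, 3 vs ≥8, 4 vs ≥9, 5 vs 10, 6 vs 10. It contains Fisher's region, so power cannot fall.

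**Step 1: the plan's own figures.** Fisher, n=10, 0.1 vs 0.6:
0.3487×0.8338 + 0.3874×0.3823 + 0.1937×0.1673 + 0.0574×0.0464 + 0.0112×0.0060 = 0.474, against 47 printed. At n=20 the same pair gives 90.8%, against 91 printed. All 30 distinct cells reproduce within 0.5 points. A one-sided 5% level does not fit (65.9% for 0.1 vs 0.6 at n=10).

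**Step 2: true size at n=10**, where the maximum is at p = 0.5:
- Fisher: 2×(1×638 + 10×176 + 45×56 + 120×11 + 210×1 + 252×1)/2^20 = 13,400/1,048,576 = 1.28%.
- Boschloo: 2×(1×848 + 10×386 + 45×176 + 120×56 + 210×11 + 252×1 + 210×1)/2^20 = 44,240/1,048,576 = 4.22%.

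At n=20 the maxima are 2.53% for Fisher and 4.64% for Boschloo.

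**Step 3: power with Boschloo.** For n=10, 0.1 vs 0.6:
0.3487×0.9452 + 0.3874×0.6331 + 0.1937×0.3823 + 0.0574×0.1673 + 0.0112×0.0464 = 0.659.

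| n per group | Rates | Fisher | Boschloo |
|---|---|---|---|
| 10 | 0.1 vs 0.5 | 29.5% | 47.1% |
| 10 | 0.1 vs 0.6 | 47.4% | 65.9% |
| 10 | 0.2 vs 0.6 | 25.3% | 42.5% |
| 20 | 0.1 vs 0.4 | 49.2% | 60.9% |
| 20 | 0.1 vs 0.5 | 74.2% | 82.2% |
| 20 | 0.2 vs 0.6 | 65.0% | 72.8% |

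Over the off-diagonal cells of Table 6-3 the gain is 3.4 to 18.5 points at n=10 and 2.9 to 11.7 points at n=20.

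**Step 4: beyond 0.6 at n=10.**

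| Rates | Fisher | Boschloo |
|---|---|---|
| 0.1 vs 0.7 | 66.7% | 82.4% |
| 0.2 vs 0.8 | 63.5% | 80.5% |
| 0.3 vs 0.9 | 66.7% | 82.4% |
| 0.1 vs 0.8 | 84.1% | 93.7% |
| 0.2 vs 0.9 | 84.1% | 93.7% |
| 0.1 vs 0.9 | 95.8% | 98.9% |

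Of the 21 pairs on the 0.1 to 0.9 grid that Table 6-3 leaves out, Fisher reaches 80% for 3 (differences of 0.7 or more) and Boschloo for 6 (differences of 0.6 or more).

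**Step 5: fewer evaluable subjects.** Fisher, 0.1 vs 0.8: 84.1% with 10 per group, 79.2% with 8, 64.8% with 7. The gain also depends on n. With 8 per group the Boschloo cut-off is 0.077 (maximum size 2.8%; the next cut-off would give 5.3%), and 0.1 vs 0.8 rises only from 79.2% to 81.2%.

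**The case against.** The strongest reply is that nothing in section 6.4.3 is wrong. The sentence on 10 per group reports what Table 6-3 shows, and there the maximum is 47%. Changing the test would not overturn it: Boschloo's maximum within the printed grid is 66%, still below 80%. A reader might infer that the sentence is an arithmetic error, or that Fisher's conservatism produces it; neither follows. Beyond 0.6 most pairs stay underpowered with either test, and the documents give no expected response rate, so contrasts of 0.6 or 0.7 are possible but not predicted. All of this stands.

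A reader might also infer that comparisons within an age cohort are abandoned. They are not: section 6.4.3 says the four groups will be compared.

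Nor should the point be carried over to adverse events. The remark in section 6.4.1 concerns sample size calculations only. Sections 6.5.3.1 and 6.5.3.2 specify counts and percentages and name no hypothesis test.

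Finally, Fisher's test is valid and familiar, and some conservatism is defensible where section 6.5 plans no multiplicity adjustment for safety or secondary endpoints. That is a reason to call the change optional. It does not remove the gain, because Boschloo's test is also exact and holds each comparison at or below 5%.

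**Conclusion.** This is a low-cost improvement to an exploratory comparison and not a correction of an error. Fisher's test uses at most 1.3% of its 5% at 10 per group and 2.5% at 20. Replacing it with Boschloo's gains up to 18.5 points within the printed grid at 10 per group and up to 11.7 at 20; those are the largest gains, and many cells gain less. The sentence on 10 per group is right for the rates tabulated and over-general beyond them: under Fisher it fails for differences of about 0.7 or more, under Boschloo for about 0.6 or more.

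The figures rest on a two-sided 5% level (supported by the reproduction of the table), 80% as the target, and 10 or 20 evaluable subjects per group. The exclusion of baseline-positive subjects in section 6.5.4 would lower the powers, most plausibly in the older cohort, which section 1.5 says may have some immunity. The allowance in Table 2 for up to 65 subjects in Part II would work the other way.

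**What to change.** In section 6.4.3:
1. Prespecify Boschloo's exact unconditional test, two-sided 5%, with outcomes ordered by the two-sided Fisher p-value, for the exploratory Part II responder-rate comparisons.
2. Recompute Table 6-3 for that test, extend the rates to 0.9, and state the level, sidedness and target power.
3. Limit the sentence on 10 per group to the differences it covers. For example: with 10 evaluable subjects per group, power is below 80% for differences of 0.5 or less on the grid, and reaches 80% only for differences of about 0.6 or more.
4. Note that exclusions under section 6.5.4 reduce these powers.

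Leave the descriptive adverse event analysis as it is.

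The cost is some wording and one recomputed table. R, which section 6.5 already lists, can run the test. No subjects, visits or procedures change. The downside is a less familiar test and slightly more computation.
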